6.1.2 Quality Control

All analyses will be conducted with the Statistical software SAS version 9.3 or higher, Stata and R. Quality control of coding and programming will be done according to the procedures applied for each database.

6.2 Protection of Human Subjects

Governance

Respective databases may have governance requirements in place to be allowed to use their data and publish the study results. This may require approval of the study protocol by external scientific bodies. For example the CPRD database studies will require Independent Scientific Advisory Committee (ISAC) approval and THIN database studies will require Scientific Committee Review (SCR) approval. The protocol will undergo internal scientific review by the MARC committee and require sign off by the GCL.

The final protocol of the Non-Interventional Study, including the final version of the Subject Informed Consent Form, must be approved or given a favorable opinion in writing by the Ethics Committee/Institutional Review Board (IRB)/Independent Ethics Committee (IEC).

The Ethics Committee/IRB/IEC must also approve any amendment to the protocol and all advertising used to recruit subjects for the study, according to local regulations.

6.2.1 Subject Informed Consent

Not applicable since this is a secondary data study.

6.2.2 Confidentiality of Study/Subject Data

NIS data will be stored in a computer database, maintaining confidentiality in accordance with the local law for Data Protection.

6.3 Communication Plan

A Publications Steering Committee has been formed for the project consisting of leading researchers in the field of diabetes, public health and epidemiology from the US, UK and Sweden.

6.3.1 Publication Plan

A Non-Interventional Study Report will be prepared within 12 months after completion of the final analytic dataset as described in the Milestones section. If step 2 is conducted the Non-Interventional Study Report will incorporate both steps.

Results for Step 1 will be presented at relevant scientific conferences and full manuscripts will be developed for publication in biomedical journals. Step 2 results will also be presented at relevant scientific conferences and published as full manuscripts

All publications will adhere to the guidelines on publications in biomedical journals established by the International Committee of Medical Journal Editors (ICMJE) and published in its Uniform Requirements of Manuscripts Submitted to Biomedical Journals. Authorship and development of publications arising from this non interventional study will also adhere to AstraZeneca's Global Publications Policy and Standard.

6.3.2 Compliance with Study Registration and Results Posting Requirements

The study will be registered on clincialtrials.gov in accordance with AZ International Procedure 8-P43-cv-X, Disclosure of Trial Information on Public Websites.

The study is not a PASS-study (neither step1 or step 2) since the step 2 analysis will only be on class level for SGLT-2 inhibitors and not able to distinguish between different NYHA categories of heart failure. Step 2 will be registered on clinicaltrials.gov.

6.3.3 Compliance with Financial Disclosure Requirements

The AZ Standard Operating Procedures will be adhered to when engaging healthcare professionals or institutions in the project.

Appendix 1. Power calculations for the secondary outcome all-cause mortality

The power calculations for the secondary outcome, all-cause mortality, are included in the table below based on a statistical power of 85% and for three scenarios with 15%, 20% and 25% risk reduction respectively. These calculations are based on a rate of all-cause mortality estimate of 0.84/100 person-years in the SGLT2 group based on CPRD data. Table 2 displays the number of person-years required in each treatment arm given either one or three controls per SGLT-2i user.

Table 2. Exposure time needed for all-cause mortality (person-years) if SGLT-2i rate is 0.84 events/100 patient-years.

Number of controls per SGLT-2i patient	Control exposure time	SGLT-2i exposure time
15% risk reduction		
1	85	85
3	70135	70135
3	138775	46258
20% risk reduction		
1	85	85
3	38858	38858
3	72933	24310
25% risk reduction		
1	85	85
3	24002	24002
3	16784	5594

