2. OBJECTIVES AND HYPOTHESES

2.1 Primary Objective(s) & Hypothesis(es)

This study has been divided in two steps where step 1 has assessed the study population length and follow up as well as comparability between SGLT-2i users and users of other diabetes medication groups. The objectives of step 1 are described in the full protocol (D1690R00015). This amendment concerns step 2 which is a comparative analysis of the risk for CV events between SGLT-2i users and a group of active comparators.

Step 2 has one primary, one secondary and two exploratory objectives and will only be conducted given that a comparative analysis is feasible based on the results from step 1. Feasibility was determined by the following requirements a) the study population has enough length of follow up, required variables of interest, and size to have sufficient power to assess the outcome of interest according to the power calculations presented in Section 5.3 and b) a suitable comparator group. Suitability of comparator groups was assessed based on the propensity score matching by applying normal requirements to assess sufficient match between different groups. This process will be outlined in more detail in the statistical analysis plan (SAP). Step 1 also informed whether analysis needed to be done on SGLT-2i class level or dapagliflozin separately applying the above-mentioned criteria. As step 2 is considered feasible based on the criteria, this protocol amendment outlines the analysis including the specifics about the treatment group, comparator group, and primary outcome, for this step. The primary, secondary and explorative objectives of the study amendment (step 2) are:

Primary objective

To compare the risk for hospitalization for heart failure between patients with T2DM who are new users of SGLT-2 inhibitors as a class versus an active comparison group including patients with T2DM who are new users of other GLD.

Secondary objective

To compare all-cause mortality between patients with T2DM who are new users of SGLT-2 inhibitors as a class versus an active comparison group including patients with T2DM who are new users of other GLD. Due to data availability this objective can only be addressed in UK and the Nordic countries.

Exploratory objectives

To estimate the incidence of acute myocardial infarction and atrial fibrillation respectively in new users of SGLT2 inhibitors and of other GLD.

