3.1.1 Data Source(s)

Several observational data sources from different countries will be included in this study to obtain a large enough population. These databases include MarketScan and Humedica databases from the United States, the DAISY database from Sweden, the DAPHNE database from Norway, the DAFFODIL database from Denmark and from the United Kingdom the Clinical Practice Research Datalink (CPRD), The Health Improvement Network (THIN), the “Diabetes Patienten Verlaufsdokumentation” (DPV) register from Germany and Manitoba Centre for Health Policy (MCHP) in Canada. AstraZeneca has access to several of these databases in-house. The databases are described more in detail in the full protocol (D1690R00015).

The contents and coverage of different variables vary between databases, therefore a set of core variables for both patient characteristics and CV events and mortality will be developed which will be described in all databases. In addition, specific variables of interest including baseline characteristics and CV events and mortality available in a limited number of the databases will also be described where appropriate.

Based on the results from the initial study (Step 1), meta-analyses for hospitalization for heart failure and all-cause mortality are feasible when including exposure-time data from all countries. However, there may not be enough subjects and person-years of exposure in the databases for each country to do standalone analyses for either endpoint. Therefore,

the analyses for these countries will be incorporated into a meta-analysis, the details of which are described below (Section 5.1).

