5.3 Sample Size and Power Calculations

Power calculations

The primary endpoint will be hospitalization for heart failure. A risk reduction in this endpoint of 20% for the SGLT-2i group compared to the control group will be considered clinically meaningful. For 85% power to detect a risk reduction of 20% with a two-sided alpha level of 0.05, and up to 1:3 treatment allocation of SGLT-2i to the comparator arm, a total of 970 events will be needed across both treatment groups and all databases after the matched SGLT-2i and control groups have been created (Table 1). This calculation assumes the background rate of hospitalization for heart failure in the standard of care group is 0.625 events per 100 person-years and assuming a 20% reduction a rate of 0.5 events per 100 person years in the SGLT-2i group. For 1:3 treatment allocation, approximately 40,842 person-years will be needed in the SGLT-2i group and 122,526 person-years will be needed in the control group. However, the key driver for the power and the analysis is the number of events. The sample size is merely an approximation of how many person-years might produce the required number of events based on the assumed event rates. Also, the ratio of SGLT-2i: control matching may vary across the databases but as long as a total of 970 events are achieved, the analysis will be sufficiently powered.

The background rate of 0.625 events per 100 person-years is relevant for US, UK and Germany based on literature and empirical rates from the databases included in the study. Based on Swedish data, a substantially higher rate of 1.58 events per 100 person years has been observed. This difference in rates could be due to the age distribution and other factors including case ascertainment and baseline cardiovascular risk.

As there may not be enough statistical power for a standalone analysis in any of the individual country databases, a meta-analysis approach will be used to conduct the treatment comparison by pooling the hazard ratio estimates from all of the databases assuming that a total of 970 events have been observed. The higher rate of 1.58 events per 100 person years may apply in Sweden and the other Nordic countries. This higher event rate allows for the possibility of a sufficiently powered analysis in the Nordics alone. If 970 events have been observed in the Nordics, then a separate analysis will be submitted

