for the Nordics database. Assuming 1:3 matching, approximately 16,019 person-years will be needed in the SGLT-2i group and 48,054 person-years will be needed in the control group to obtain the target of 970 events.

Table 1 displays the target number of events and total exposure time (in person-years) needed for the SGLT-2i and control groups under different estimates for risk reduction, power, and SGLT-2i: control treatment allocation ratios :

Table 1. Exposure time needed for hospitalization for heart failure (person-years) if SGLT-2 rate is 0.5 events/100 patient-years.

Number of controls per SGLT-2i patient	Number of events			Total exposure time (SGLT-2i + control)			SGLT-2i exposure time		
	80	85	90	80	85	90	80	85	90
30% reduction									
1	255	290	340	42000	47765	56000	21000	23882	28000
3	340	380	460	51459	57514	69622	12865	14378	17405
5	470	545	610	69263	80316	89895	11544	13386	14982
25% reduction									
1	385	440	515	66000	75429	88286	33000	37714	44143
3	520	600	700	83200	96000	112000	20800	24000	28000
5	710	790	940	111130	123652	147130	18522	20609	24522
20% reduction									
1	635	730	850	112889	129778	151111	56444	64889	75556
3	850	970	1160	143158	163368	195368	35789	40842	48842
5	1160	1350	1520	192000	223448	251586	32000	37241	41931
15% reduction									
1	1195	1370	1600	219622	251784	294054	109811	125892	147027
3	1620	1870	2120	286130	330286	374442	71532	82571	93610
5	2220	2500	2900	387077	435897	505641	64513	72650	84274

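### Appendix 1, Table 2: the 25% / 1:3 mortality row gives about 235 deaths and 48% power, not the stated 85%

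*Combined protocol and SAP*

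**What the plan says.** Appendix 1 gives the only power calculation for all-cause mortality, the single secondary outcome. The calculations are "based on a statistical power of 85% and for three scenarios with 15%, 20% and 25% risk reduction respectively". They start from a "rate of all-cause mortality estimate of 0.84/100 person-years in the SGLT2 group based on CPRD data", and Table 2 gives the person-years per arm "given either one or three controls per SGLT-2i user".

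In the text as extracted, the row labels of Table 2 are shifted, because the power header (85) occupies the first line of each block. The rows can still be identified: in each block one pair of figures is equal (1:1) and the other is in a 3:1 ratio (1:3). For a 25% reduction the pairs are 24,002 / 24,002 and 16,784 control / 5,594 SGLT-2i.

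Section 5.3 sets out the matching calculation for heart failure hospitalization: "Table 1 displays the target number of events and total exposure time (in person-years) needed for the SGLT-2i and control groups". For 25% reduction, 85% power and 1:3, Table 1 gives 600 events.

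On feasibility, Section 3.1.1 says that "meta-analyses for hospitalization for heart failure and all-cause mortality are feasible when including exposure-time data from all countries". Section 2.1 says of the mortality objective: "Due to data availability this objective can only be addressed in UK and the Nordic countries". The synopsis (Outcomes) and Section 4.2 carry the same restriction.

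**The concern.** The 25% / 1:3 row stands out before any formula is applied. Unequal allocation is less efficient per event, so moving from 1:1 to 1:3 should lower the SGLT-2i exposure but raise the total. Table 1 behaves this way throughout, and so do the 15% and 20% blocks of Table 2. In the 25% block the total falls by more than half.

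The table tells the reader how much exposure supports a mortality comparison of a given size. Someone using this row would believe that about 5,600 SGLT-2i person-years suffice for a 25% reduction, when that exposure gives roughly an even chance of detecting it.

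**Working it through.** **Inputs**
- SGLT-2i death rate r1 = 0.0084 per person-year (Appendix 1).
- Control rate r0 = 0.0084 / 0.75 = 0.0112. Section 5.3 uses the same convention for the primary endpoint (0.5 against 0.625 for a 20% reduction).
- Hazard ratio 0.75, power 85%, k = 3 controls per SGLT-2i user (Appendix 1).
- Two-sided alpha 0.05. Section 5.3 states it for the primary endpoint ("with a two-sided alpha level of 0.05, and up to 1:3 treatment allocation of SGLT-2i to the comparator arm"); using it for mortality is an assumption.

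**Reproducing the plan's conversion.** SGLT-2i person-years = events / (r1 + k × r0).
- Table 1, 25% / 1:3 / 85%: 600 / (0.005 + 3 × 0.006667) = 24,000, as printed.
- Table 2, 20% / 1:3, with Table 1's 970 events: 970 / (0.0084 + 3 × 0.0105) = 24,311 SGLT-2i and 72,932 control. The printed figures are 24,310 and 72,933.

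So the conversion is known, and at least one Table 2 row comes from Table 1's event count.

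**The 25% / 1:3 row as printed**
- Deaths = 5,594 × 0.0084 + 16,784 × 0.0112 = 47.0 + 188.0 = 235.
- Schoenfeld power = Φ(√(235 × 0.25 × 0.75) × |ln 0.75| − 1.960) = Φ(6.638 × 0.2877 − 1.960) = Φ(−0.050) = 48%.

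**What 85% needs**
- Deaths = (1.960 + 1.036)² / (0.1875 × (ln 0.75)²) = 578.6, or 579.
- Person-years = 578.6 / 0.042 = 13,776 SGLT-2i and 41,328 control (13,786 and 41,357 with 579 deaths).
- With Table 1's 600 events: 600 / 0.042 = 14,286 SGLT-2i and 42,857 control.
- Shortfall: 13,776 / 5,594 = 2.46; 14,286 / 5,594 = 2.55.

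**All six rows of Table 2**

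| Reduction | Ratio | Total person-years | Implied deaths | Schoenfeld power | Table 1 events (85%) |
|---|---|---|---|---|---|
| 15% | 1:1 | 140,270 | 1,282 | 82.9% | 1,370 |
| 15% | 1:3 | 185,033 | 1,760 | 83.9% | 1,870 |
| 20% | 1:1 | 77,716 | 734 | 85.6% | 730 |
| 20% | 1:3 | 97,243 | 970 | 85.3% | 970 |
| 25% | 1:1 | 48,004 | 470 | 87.7% | 440 |
| 25% | 1:3 | 22,378 | 235 | 48.0% | 600 |

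**Sensitivity to method.** For the printed 25% / 1:3 row, power is 42% with a Wald test of the log rate ratio, 48% with a rate difference, 60% with one-sided 0.05, and 38% (176 deaths) if 0.84 is read as the control rate. Across the other formulas tried for 85% power at two-sided 0.05, the requirement is about 12,000 to 16,100 SGLT-2i person-years. The printed exposure gives 85% power only for a reduction of about 35% (hazard ratio about 0.65).

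**The case against.** The best defence concerns consequence, not arithmetic. Nothing in the plan sizes, triggers or stops an analysis on this row. The event target is 970 heart failure hospitalizations, and the study period runs to the latest data in each source (Section 3.1). Mortality will be reported as a hazard ratio with a 95% confidence interval, which shows the precision actually achieved. The 25% reduction is one of three scenarios. The only effect called clinically meaningful is 20%, for the primary endpoint, and both 20% rows reproduce.

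Other exposure figures in the plan also exceed the corrected need. At a hazard ratio of 0.75 and the appendix's death rate, the 20% / 1:3 row would give about 1,021 deaths and 98% power. The Nordic-only figure in Section 5.3 (16,019 and 48,054 person-years) would give about 673 deaths and 90% power, if that exposure is reached.

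All of this stands. A reader might infer that the mortality analysis itself will be underpowered, or that the sponsor would declare it adequate on about 40% of the exposure needed and over-interpret a null result. The documents do not support that, because no decision rests on this cell.

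Nor do they support treating the whole table as unreliable. The other five rows lie within about 3 points of 85%, and the plan does not state the formula behind either table. The Section 3.1.1 wording is likewise no sign that deaths would be drawn from the US, Germany or Canada, since three other places exclude that.

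A broken table in the extracted text is not a convincing explanation. The two figures keep their 3:1 ratio, which a digit lost from one cell would destroy.

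**Conclusion.** The row is wrong as printed: about 235 deaths and 48% power against a stated 85%, with required exposure understated about 2.5-fold. This rests on the appendix's rate of 0.84 per 100 person-years in the SGLT-2i group, a hazard ratio of 0.75 and the two-sided 0.05 level borrowed from Section 5.3. No alternative tried brought power above 60%. The fall in total exposure from 1:1 to 1:3 shows the inconsistency without any of those assumptions.

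The exact replacement depends on the method. Schoenfeld gives about 13,780 / 41,330 person-years and Table 1's 600 events give 14,286 / 42,857. Among the Table 2 rows, only 20% / 1:3 matches Table 1's event count exactly, so neither pair can be called the sponsor's intended figure.

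The error affects a planning figure for the secondary endpoint and should be fixed. The Section 3.1.1 sentence is a real but minor inconsistency of wording.

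**What to change.** - Recompute the 25% / 1:3 row of Table 2. State the formula and alpha, and print the number of deaths. Expect about 579 to 600 deaths, that is about 13,800 to 14,300 SGLT-2i and 41,300 to 42,900 control person-years (14,286 / 42,857 if Table 1's 600 events are used).
- When the table is rerun, check the other five rows for consistency with the stated method. They need nothing more.
- In Section 3.1.1, separate the two outcomes and base the mortality feasibility statement on UK and Nordic exposure only.

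The cost is one table row, a method note with event counts, and one sentence. Data collection, the primary analysis and the 970-event target do not change.
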